1.0 Objectives

The **primary aim** of this proposal is to use a **phase II randomized controlled trial** to compare the **intervention of a second regional anesthetic block (QL block) versus usual care** (single intraoperative QL block) to **increase the proportion of opioid-free pancreatic cancer survivors** at discharge after potentially curative surgery. The primary outcome measure will be the proportion of patients in each arm who are opioid-free at discharge and thus not requiring any opioids on their discharge prescription. **Both arms will include a standardized non-narcotic bundle** for pain control supplementation during hospital stay and upon discharge and previously published enhanced surgical recovery protocols, based on pancreatic leak risk.

PICO: In patients undergoing open pancreatectomy using general anesthesia with regional pain block (QL block with 72-hr liposomal bupivacaine) [**Patients**], can the placement of a 2nd QL block (on postoperative day 4) [**Intervention**] more effectively wean patients off opioids during the inpatient stay vs. usual care of QL block (both arms with low-dose IV-PCA with non-narcotic bundle) [**Control**]. The primary outcome measure will be the proportion of patients able to be opioid free on discharge prescriptions [**Outcome**].

Outcome Measures:

Primary:

- **Proportion of patients** totally free of opioids on discharge, requiring no opioid prescription.

Secondary:

- **Hospital Measures**
 - Total oral morphine equivalents (OME) mg – which arm is lower and what effect size difference
 - Cost [hospital charges x cost/charge ratio] and cost-benefit analysis
 - Patient Reported Outcomes for gastrointestinal surgery– MD Anderson Symptom Inventory (MDASI-GI) for Patient-Reported Outcomes
- **Discharge Measures**
 - Actual initial discharge pain prescription dosage/size [CDC recommendation is <200mg after surgery]
 - % patients with initial discharge Rx dosage/size total OME <200mg
 - % patients using opioids on POD 30
 - MDASI-GI in clinic visits
 - % pts using opioids at POD 90
 - Total OME for first 30 days and first 90 days [inpatient + outpatient]
 - 6-mo and 1-yr follow-up – pts and family free of opioid use

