4.0 Research Plan and Methods

This is a **single-center phase II open-label randomized controlled trial** to assess the effect of an additional QL block on POD4 in patients undergoing pancreatic surgery with potentially curative intent. The primary endpoint is the proportion of patients who are **opioid-free on the discharge date**. Patients will be randomized with 1:1 ratio to receive either QL in OR + non-narc bundle +/- low-dose IV-PCA (control arm) or QL in OR and QL on POD4 AM + non-narc bundle +/- low-dose IV-PCA (experimental arm). The **allocation will be concealed until postoperative day 1** so that clinicians at the time of surgical consent will not be able to predict to which pathway the next enrollee will be assigned. Patients will be stratified based on pathway allocation (Green vs. Orange vs. Blue) and preoperative average daily OME use in the past 7 days (>5 mg vs. ≤ 5 mg OME).

Our **3 colored pathways are based on clinical predictors of pancreatic leak risk and thus median length of stay**. The median length of stay for Green (low-risk pancreaticoduodenectomy), Orange (high-risk pancreaticoduodenectomy), and Blue (distal pancreatectomy) patients is 6, 8, and 5 days, respectively. The length of stay affects the weaning, in that longer stays allow more time to wean off inpatient opioid use.

Method of Group Assignment and Randomization

Sequence Generation: Redcap will be used for 1:1 allocation with stratification for **postoperative pathway (Green, Orange, or Blue) which is determined preoperatively based on risk of pancreatic leak** and preoperative average daily OME use in the past 7 days (>5 mg vs. ≤ 5 mg OME).

Allocation Concealment and Mechanism: Allocation will be concealed at the time of enrollment from patients, providers, and researchers.

Implementation: Acute pain team, surgeons, advanced practice providers, fellows, and nurses will perform interventions and assessments per standard of care.

Blinding: All clinicians and patients will be **blinded from the allocation before surgery, intraoperatively, and until POD1**. The only difference in intervention will be the 2nd QL block which cannot be blinded.

Intervention Strategy:

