 - Patients' daily pain scores (checked by nurses q4hr) will be used to ensure that adequate pain control prescribed before discharge. There is no "threshold" score that will be used since one patient's "4" is different than another patient's "4," but the trend will be useful to ensure patients are not being ignored. More importantly, all patients will be judged by their activities of daily living on the last 24hrs to ensure pain control is adequate.
 - **The number of opioid pills will be formulaic to avoid bias by clinicians or patients in one arm or the other - we will take the last 24hrs of inpatient opioid pills used and multiply by a factor of 5 days to make this number standardized between the 2 arms.**
 - **Both arms get the same non-narcotic pain management bundle for inpatient and discharge.**
- **Prospective AE Records**
 - Inpatient advanced practice providers (nurse practitioner or physician assistant) will document complications daily prospectively
 - **Hospitalization, 30-day, and 90-day complications prospectively recorded** into our Pancreas Surgery Database RCR01-112 systematically on a weekly basis with faculty attendance
 - **We record all complications for 90 days after all operations using our faculty-led weekly review. Therefore we plan to ask for DSMB waiver since we are not doing any experimental procedure or using any new drug.**
- **Safety Review**
 - If the analysis of the first 20 patients yields complication rates from the intervention arm above the *pre-determined acceptable level*, the study will be terminated. This level is at least 25% of patients requiring deviation from their usual pathway and anticipated stay.

[figure not shown]

Figure 2. Study intervention timeline

| | Pre- Op Days | Inpatient Postop Day | | | | | | | | | | | Outpatient Month ^{a, b} | | | |
|------------------------------------|--------------------|----------------------|-------------|---|---|---|---|---|---|---|----------------|----|-------------------------------------|---|---|----|
| | | -30 to 0 | PACU "0" | 1 | 2 | 3 | 4 | 5 | 6 | 7 | 8 | DC | 1 | 3 | 6 | 12 |
| Oral Morphine Equivalents | X | X | X | X | X | X | X | X | X | X | X | X | X | X | X | X |
| MDASI-GI | X | | | | | X | | | | | X ^c | X | | X | X | |
| Pain Score | X | X | X | X | X | X | X | X | X | X | X | | | | | |
| Hospital Cost | | | | | | | | | | | X | | | | | |
| Adjuvant Therapy [if needed] | | | | | | | | | | | | X | | X | X | |

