5.0 Statistics and Justification of Sample Size

For the primary analysis, we will perform Chi-squared test to compare the proportion of patients who are opioid-free on the discharge date between the two arms. As a secondary analysis, we will also perform the Cochran–Mantel–Haenszel test to take into account the stratification factors. In addition, stratified logistic regression analysis will be carried out to assess the difference between the two arms after adjusting for the stratification factors and other patient characteristics at baseline. Similar analyses will be performed for other binary secondary outcomes, such as discharge Rx dosage/size total OME <200mg (yes vs. no), opioids usage on postoperative days 30, 90, 180, and 365 (yes vs. no), etc. Two sample t-test or Wilcoxon rank-sum test will be used to compare continuous secondary outcomes such as total inpatient OME, cost, QOL scores, pain prescription dosage at first discharge, etc. Other statistical analyses may be performed as appropriate.

Based on historical data, we anticipate that 5% patients in the control arm will be opioid-free in their discharge prescriptions, while with the additional TAP block in the experimental arm, it will increase the proportion to 25%. Under this assumption, the study will require 106 **patients (53 per arm)** in order to have 84.5% power to detect such a 20% difference, using two-sided Chi-squared test and with 5% significance level. East6.3 was used for the sample size calculation. Assuming a liberal 10% dropout rate, a total of 118 patients will be enrolled from our single institution. Based

on our historical operation volume of 120 patients per year, we anticipate the ability to complete enrollment within 1 year of opening the protocol. One interim analysis will be performed when half of the patients (N=53) have been randomized and received treatment. The trial will be stopped due to futility if the p-value is >0.774 .

- Power and significance: 84.5% power ($\beta=0.155$) and $\alpha=0.05$ (two-sided)
- Baseline estimate of control group with no opioids on discharge day: **5%**
- Estimate of experimental: **25%**
- Sample size per arm: 53 pts
- Assume 10% dropout: 59 per arm
 - [1 year to complete enrollment]

In order to enroll the total 118 patients, we will screen up to 140 patients in order to account for screen failures and those who are ineligible due to aborted surgeries.

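### Continuous secondary outcomes get only unadjusted tests, although baseline values are collected and binary outcomes are adjusted; total inpatient OME also lacks one named test and an effect estimate

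*Combined protocol and SAP*

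**What the plan says.** Section 5.0 tests the primary outcome by chi-squared. As supporting analyses it adds a Cochran–Mantel–Haenszel test on the stratification factors and a logistic regression adjusted for those factors and other baseline characteristics. The same set carries over to the rest of the yes/no outcomes: "Similar analyses will be performed for other binary secondary outcomes".

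For continuous outcomes the text is: "Two sample t-test or Wilcoxon rank-sum test will be used to compare continuous secondary outcomes such as total inpatient OME, cost, QOL scores". Neither test uses a baseline value or a stratification factor, and no rule says which test applies to which outcome. The only other provision is "Other statistical analyses may be performed as appropriate".

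The data for adjustment are already planned:

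- Section 4.0 states: "Patients will be stratified based on pathway allocation (Green vs. Orange vs. Blue) and preoperative average daily OME use in the past 7 days".
- The schedule in Figure 2 marks both MDASI-GI and OME in the preoperative column. The OME row opens "Oral Morphine Equivalents | X | X".
- Section 1.0 lists, as a secondary outcome, "Total oral morphine equivalents (OME) mg – which arm is lower and what effect size difference".
- Section 2.0 gives the historical total OME of IV-PCA patients as median 525 mg, range 28–4,362 mg.

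**The concern.** Two separate gaps sit in one sentence of Section 5.0.

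**Adjustment.** The plan treats pathway and preoperative OME as important enough to stratify on and to adjust for in binary outcomes, then leaves them out of every continuous outcome. MDASI-GI has a true preoperative measurement of the same quantity, and the named tests ignore it. With 53 per arm, the chance difference in baseline means has a standard error of √(2/53) = 0.19 SD (95% range about ±0.38 SD). The test allows for that variation, but an adjusted model would remove the part that predicts outcome.

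**Test and estimate for OME.** On a strongly skewed outcome, a t-test and a Wilcoxon test answer different questions and can disagree. The choice is open, and no effect estimate or interval is named although Section 1.0 asks for an effect size.

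These outcomes show whether the second block lowers inpatient opioid exposure and symptoms. At stake is how precisely and credibly that is answered. The primary conclusion is not affected.

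**Working it through.** **1. The plan's own figure.** Inputs from Section 5.0: 5% against 25%, 53 per arm, two-sided 0.05. With unpooled variance, SE = √[(0.05×0.95 + 0.25×0.75)/53] = 0.0666, and power = Φ(0.20/0.0666 − 1.96) = 85.2%. Pooled variance gives 83.2% and exact enumeration of the chi-squared test 85.9%, against 84.5% stated. At 84.5% power the unpooled formula gives 52.004, so 53 per arm; 106/0.9 rounds up to 118. The design reproduces, and nothing below changes it.

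**2. Baseline adjustment (MDASI-GI).** The documents give no SD and no correlation ρ between baseline and outcome. Both ρ and the 0.5 SD difference are therefore assumptions. Power is from the noncentral t with 53 per arm; adjustment multiplies the SD by √(1 − ρ²). The simulated column is ANCOVA with four covariate terms (baseline, two for pathway, one for OME group) in 30,000 trials of 106 patients. It assumes a 40/30/30 pathway mix, 20% above 5 mg, and strata that are not prognostic.

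| ρ | Power, formula | Power, simulated ANCOVA | Detectable at 80% power (SD, formula) | Equivalent unadjusted total, 106/(1 − ρ²) |
|---|---|---|---|---|
| 0 (t-test) | 72.2% | – | 0.549 | 106 |
| 0 | – | 71.7% | – | – |
| 0.1 | 72.7% | 72.0% | 0.547 | 107 |
| 0.2 | 74.0% | 73.8% | 0.538 | 110 |
| 0.3 | 76.2% | 76.0% | 0.524 | 116 |
| 0.5 | 83.8% | 83.3% | 0.476 | 141 |
| 0.7 | 94.6% | 94.4% | 0.392 | 208 |

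In the same simulated trials the t-test had 72.3–72.6% power, so the worst case is a loss of about 0.6 points. ANCOVA type I error was 4.7–5.0%.

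**3. Strata alone.** Section 4.0 says: "The median length of stay for Green (low-risk pancreaticoduodenectomy), Orange (high-risk pancreaticoduodenectomy), and Blue (distal pancreatectomy) patients is 6, 8, and 5 days". The note under Figure 2 gives 7 for Orange, so both values were tried. If OME scaled with median stay, the variance of ln(stay) would be 0.017–0.037. Divided by a log variance of about 0.9–1.0, pathway would explain about 2–4%, giving 71.7–72.8% power against 72.2%. That is effectively no gain.

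**4. Scale and test for OME.** Inputs: median 525, minimum 28, maximum 4,362 mg (Section 2.0). The number of IV-PCA patients behind the range is not given, so n = 100–158 is assumed; the expected normal range is then 5.02–5.34 SD.

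- *Symmetric log-normal.* ln(4362/28) = 5.05; divided by 5.02–5.34 this gives a log SD of 1.01–0.95.
- *Split-normal on the log scale, matching all three figures.* ln(525/28) = 2.93 below the median and ln(4362/525) = 2.12 above. Divided by half the expected range (2.51–2.67), these give log SDs of about 1.17–1.10 below and 0.84–0.79 above.

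Simulated with 53 per arm and an assumed 40% lower median:

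| Shape | t-test on mg | t-test on log | Wilcoxon | mg t-test and Wilcoxon disagree at p<0.05 |
|---|---|---|---|---|
| Split-normal | 69–75% | 73–78% | 72–77% | 15–17% |
| Symmetric log-normal | 55–61% | 74–78% | 72–76% | 22–25% |

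The log scale gains about 3–4 points over mg in the first row and about 16–19 in the second. With no true effect, reporting whichever of the mg t-test and Wilcoxon is significant gives about 7% false positives.

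**The case against.** The strongest reply is that the planned tests are valid under randomisation, concern secondary outcomes with no power target in a phase II trial, and leave the primary conclusion and sample size untouched. All of that stands.

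**The contrast with binary outcomes has limits.** The lead test for those outcomes is itself unadjusted, so parity needs only an adjusted model beside the planned test. This stands, and the fix asks for no more.

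**The gain is uncertain.** It rests on an assumed correlation and is small at 0.3 or below. Preoperative daily OME is not the same quantity as an inpatient total and is already balanced at the 5 mg cut. This stands too; the case for adjustment is strongest for MDASI-GI.

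**The OME distribution is poorly known.** A reader might infer from the historical range that a t-test on mg would forfeit 16–19 points of power. The documents do not support that as a finding. The reported median lies above the geometric midpoint of the range (√(28×4362) ≈ 349 mg), so a symmetric log-normal centred on 525 mg exaggerates the upper tail. Two extremes are weak evidence of shape. The figures also predate the changes to usual care described in Section 2.0, and IV-PCA is optional in the trial.

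**The effect size.** Section 5.0 does not say that only a p-value will be reported, and a t-test comparison yields a mean difference. A ratio of geometric means is also not a difference in mg. Both are fair. What remains is that no estimate or interval is named, and a Wilcoxon p-value alone supplies none.

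The catch-all sentence does not answer the point: it allows an adjusted analysis but commits to no model, covariate or outcome.

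**Conclusion.** The point holds as an improvement in efficiency and prespecification for secondary outcomes. It is not a validity error, and a reader should not infer that the planned tests are biased or that the primary analysis needs changing: the chi-squared test is valid, and the sample size was computed for it.

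For MDASI-GI, adjustment is worth between nothing and about 22 points of power (94.6 − 72.2) across the assumed correlations, with a worst-case cost of about 0.6 points. The gain becomes material at a correlation of about 0.5 or more.

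For total inpatient OME, naming the analysis and the estimate matters more than the covariates. The open choice is the main weakness: 15–25% disagreement between the tests under an assumed 40% lower median, and about 7% error if the significant one is picked. The power advantage of the log scale depends on the assumed shape, and nothing in the documents fixes that shape. Strata adjustment alone adds almost nothing.

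**What to change.** Add to Section 5.0, before any outcome data are seen by arm:

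- **MDASI-GI:** ANCOVA at a named visit, or a mixed model over visits, with the preoperative score, pathway and preoperative OME group. Enter the factors as main effects (three parameters). Report the adjusted mean difference with 95% CI.
- **Total inpatient OME:** name one analysis, either a log-scale linear model with a stated rule for zeros or a rank-based method. Include pathway and preoperative OME as covariates. Report an effect estimate with 95% CI, such as a ratio of geometric means for the log-scale model or a Hodges–Lehmann shift in mg for the rank-based method.
- **Not to be used as covariates:** actual length of stay, and OME used once allocation is known. Staff and patients are "blinded from the allocation before surgery, intraoperatively, and until POD1", so both can be affected by the arm.
- **Test named per outcome:** state whether the t-test or the Wilcoxon applies to each continuous outcome. The adjusted model may sit beside it, as the binary outcomes already do. Strata adjustment for cost and discharge prescription size is optional.
- **Primary chi-squared test:** unchanged.

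The cost is a few sentences of SAP text and minor programming, with no new patients, visits or data.

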2.0 Rationale

There is increasing evidence that an elective surgical event is often a patient's initial and greatest exposure to opioids.¹⁻³ In survivors of cancer surgery, persistent opioid use can be predicted by the dispensed amount of a patient's initial outpatient prescription at surgical discharge.^{1,4,5} Furthermore, national prescribing pattern data have shown that the initial outpatient prescription of *oral morphine equivalents (OME)* can be predicted by opioid utilization during the last 24hrs in the hospital.^{6,7} A tangible contribution from the surgical community would be the active implementation of a protocol to eliminate or reduce outpatient opioid dissemination in a

greater proportion of cancer survivors after oncologic surgery. In this context, we have implemented regional anesthetic techniques including ultrasound-guided four-point *bilateral quadratus lumborum (QL) block using 72-hr liposomal bupivacaine*. Despite the success of reducing our median length of stay from 10 days to 6 days with enhanced recovery protocols in 2016-17, only 5% of our patients were discharged without opioids after review of 158 consecutive pancreatectomy patients. Median initial outpatient prescription OME was 316mg, far above the 200mg OME recommended by the Centers for Disease Control.⁸ We thus see an opportunity to improve rapid postoperative opioid weaning to increase the proportion of opioid-free patients at surgical discharge. We hypothesize that a second, repeat QL block on postoperative day 4 will bridge the gap between the initial intraoperative QL block and ambulatory status, and increase the proportion of cancer survivors without postoperative outpatient opioid prescriptions. **Rescue blocks are currently used on an as-needed basis** only when the first block is insufficient or if the clinical team decides that the opioid use is subjectively too much. **We have not routinely used a 2nd block, because opioid-free discharge has never previously been a goal.** Our new goal is to **reduce dissemination of opioids into the community and reduce the risk of persistent opioid use among survivors.**

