“Enhanced recovery after surgery,” or ERAS, is no longer a novel idea. However, its benefits are beginning to be seen beyond the early metrics of hospital stay and activities of daily living. Downstream benefits have included reduced complications, less readmissions (despite earlier discharges), less hospital resource consumption (cost), and improved postoperative quality of life. With the opioid epidemic increasingly discussed in both medical and lay literature, we are seeking to modify our enhanced recovery program in abdominal cancer surgery to reduce opioid exposure in the hospital. Medical literature has shown that oftentimes the first exposure or greatest exposure to opioids comes from an elective surgical event. Persistent opioid use (past 1yr) can be predicted by the size of a patient’s initial outpatient prescription **oral morphine equivalents (OME)**. And the **initial outpatient prescription OME can be predicted by the amount of opioids used in the last 24hrs of hospitalization**.

We recently analyzed 158 consecutive pancreatectomy patients’ opioid use by converting units into OME using an automatically generated download from our electronic health record. In our analysis, we found that intravenous patient-controlled anesthesia (IV-PCA) represented the largest contributor to total inpatient OME, even when universally paired with an ultrasound-guided regional anesthetic block with 72-hr liposomal bupivacaine. Median total OME (from all sources of pain control) for patients with IV-PCA was 525mg (range 28-4,362mg). Median OME contribution from IV-PCA alone was 373mg. **Only 5% of patients were discharged without opioids.** Median initial outpatient prescription OME was 316mg, far above the 200mg OME recommended by the CDC. We thus see an **opportunity to reduce opioid exposure** to increase the **proportion of opioid-free patients at discharge**. We are already embarking in improving our “usual care” enhanced surgical recovery bundle by using standardized non-narcotics and reducing initial IV-PCA settings.

HYPOTHESIS

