On postoperative day 4 [at least 96hrs from initial QL on postoperative day “0”, which is the day of surgery, per FDA guidelines], patients will undergo a 2nd QL procedure in the regular hospital room by the Acute Pain Service attending anesthesiologist using ultrasound guidance, which is usual routine method. The intent will be to do the 2nd QL.

This will be a **Type I QL block**, which allows an anterior approach to the correct fascial layers. Using sterile technique, the attending anesthesiologist will guide the needle through the appropriate skin, subcutaneous, and muscle layers to find the right fascial plane **using ultrasound localization**. The risk of complications is virtually nil, because most hospital subcutaneous and intramuscular shots which are done blindly or by “landmark,” the QL block will be done by exact ultrasound guidance. **This block will only be done by Acute Pain Service certified attendings.** We are not studying this block’s mechanism or the drug’s mechanism – both of which are well documented in 1000’s of patients. **This RCT focuses on the novel timing of using this regional block to augment the opioid weaning process.**

Patients or providers may choose to forego the option if patients are already opioid-free or nearly opioid-free. If the patient is discharged before POD4, there will not be any 2nd injection. The **usual measures of non-narcotic bundle** [including acetaminophen, NSAIDs, muscle relaxers, and Lidocaine-secreting patches] and conversion from IV pain meds to oral pains will be done to reduce total opioid exposure and use.

The 2nd block is a “Rescue Block” which we currently utilized on the floor for patients with pain control that is not making the anticipated progress on postoperative day 4, and if we want to avoid opioids due to traditional issues like ileus, somnolence, and nausea. Thus, in terms of hospital billing, this is still within the realm of usual care. It is not experimental therapy.

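### Does fixing N at 106 on a historical 5% control rate, with no check of that rate at the interim look, leave the trial underpowered?

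*Combined protocol and SAP*

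**What the plan says.** The sample size in section 5.0 rests on "Based on historical data, we anticipate that 5% patients in the control arm will be opioid-free in their discharge prescriptions", rising to 25% in the experimental arm. With 53 per arm and a two-sided 5% chi-squared test, the trial is sized "in order to have 84.5% power to detect such a 20% difference". Section 5.0 ties that power explicitly to the two assumed rates. Allowing 10% dropout, 118 patients are enrolled.

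Section 2.0 gives the source of the 5%: "only 5% of our patients were discharged without opioids after review of 158 consecutive pancreatectomy patients". It also says that the centre is already improving its usual-care "enhanced surgical recovery bundle by using standardized non-narcotics and reducing initial IV-PCA settings". Section 4.0 gives both arms the same non-narcotic bundle and low-dose IV-PCA, and sets the discharge opioid count by a formula based on the last 24 hours of use.

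On monitoring, section 5.0 says "One interim analysis will be performed when half of the patients (N=53) have been randomized and received treatment", with a stop for futility if p exceeds 0.774. The review of the first 20 patients in section 4.0 concerns complications only. Neither section provides for checking the opioid-free rate or recalculating N.

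On feasibility, section 5.0 cites a "historical operation volume of 120 patients per year", expects to finish enrolment within one year, and states that "we will screen up to 140 patients".

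**The concern.** The one input that fixes N appears to describe care that the trial no longer gives. A standardized bundle, lower IV-PCA settings, a formula-based prescription and a new opioid-free goal could each raise the control rate above 5%. The variance of a proportion grows as it moves towards 50%, so a 20-point gain becomes harder to detect. Section 4.0 adds a second reason: "Patients or providers may choose to forego the option if patients are already opioid-free or nearly opioid-free". The block can then help only the remaining patients, and a higher control rate leaves fewer of them.

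The endpoint is known at discharge, so the rate with both arms combined would be available at the interim look without new data. If the control rate were 15%, the trial would run to 106 patients and miss a true 20-point benefit about 32% of the time, not the planned 15.5%. Nothing in the plan would prompt a response.

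**Working it through.** **Inputs.** From section 5.0: 5% versus 25%, 53 per arm, two-sided alpha 0.05, chi-squared test, one look at 53 with a stop if p > 0.774, 10% dropout, 120 operations per year, screening limit 140. From section 2.0: 5% of 158. Control rates other than 5% are assumptions; the documents give none.

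**1. The plan's own figure.**
- Pooled variance: z = [0.20√53 − 1.96√(2 × 0.15 × 0.85)] / √(0.05 × 0.95 + 0.25 × 0.75) = (1.456 − 0.990)/0.485 = 0.96, power 83.2%.
- Unpooled variance: 0.20/√(0.235/53) − 1.96 = 1.04, power 85.2%; with the futility stop, 84.4%.
- Exact enumeration of the uncorrected chi-squared test: 85.9%.
- Enrolment: 106/0.9 = 117.8, so 118.

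The stated 84.5% and 118 are reproduced.

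**2. Sampling error in the 5%.** Taking 8 of 158 (count inferred from 5%), the exact 95% interval is 2.2% to 9.7%. Power for a 20-point gain at those ends is 93.8% and 76.0%.

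**3. Power at other control rates** (53 per arm, exact). Three readings of the same planned effect: a gain of 20 points; conversion of 0.20/0.95 = 21.1% of patients not otherwise opioid-free; an odds ratio of (0.25/0.75)/(0.05/0.95) = 6.33.

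| Control rate | +20 points | 21.1% converted | Odds ratio 6.33 |
|---|---|---|---|
| 2% | 94.3% | 95.2% | 50.4% |
| 5% | 85.9% | 85.9% | 85.9% |
| 10% | 75.5% | 71.5% | 97.4% |
| 15% | 68.4% | 59.7% | 99.1% |
| 20% | 62.9% | 49.8% | 99.5% |

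The sign of the change in power depends on the effect scale and on the direction of the rate, and the documents settle neither.

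**4. What a pooled-rate rule would do.** The plan implies (5% + 25%)/2 = 15% pooled, about 8 of 53. Consider a rule triggered at 11 of 53 when futility is not met, with n per arm = (1.960 + 1.015)² × [pc(1 − pc) + pe(1 − pe)]/0.20², where pc and pe are the pooled rate minus and plus 0.10, a floor of 53 and a cap of 80. It gives 53 at a pooled 15%, 67 at 20% and 79 at 25%. Simulated power, futility look kept:

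| True rates | Fixed N | With rule |
|---|---|---|
| 5% v 25% | 85.4% | 86.1% |
| 10% v 30% | 74.8% | 79.6% |
| 15% v 35% | 67.5% | 77.8% |
| 20% v 40% | 61.9% | 75.7% |
| 10% v 28.9% (21.1% converted) | 70.9% | 75.6% |
| 15% v 32.9% (21.1% converted) | 59.0% | 68.8% |
| 20% v 36.8% (21.1% converted) | 49.0% | 61.7% |
| 10% v 25% | 53% | 57% |
| 2% v 11.4% (odds ratio 6.33) | 49% | 49% |

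In the first four rows the chance of enlargement is 15%, 49%, 77% and 89%.

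- On the conversion scale the rule recovers 4.7 of 14.5, 9.8 of 26.4 and 12.7 of 36.4 points lost relative to 85.4%: about a third.
- If 5% versus 25% is right, mean evaluable N rises from 105 to 111. The trials that are enlarged go to at least 138 and average 146 (146/106 = 1.38), although under fixed N those trials already had 93% power.
- At 5% versus 35%, where fixed-N power is already 98.6%, half of trials are enlarged. The pooled rate cannot tell a high control rate from a large effect.
- At a 2% control rate with odds ratio 6.33, the trigger is met in 0.04% of trials.

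**5. Cost at the cap.** 160 evaluable is 160/106 = 1.51 times the plan. Enrolled: 160/0.9 = 178. Screened at the plan's ratio: 178 × 140/118 = 211, against a limit of 140. At 120 operations per year, 178/120 = 1.5 years and 211/120 = 1.8 years, against one year.

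**The case for a change.** The strongest case for a change is that the target is stated as a difference of 20 percentage points, and the option to skip the block makes a constant odds ratio hard to believe. At a 15% control rate, holding 6.33 needs 44.4% of the remaining patients converted, twice the planned 21.1%. On the two more natural scales, power falls as the control rate rises. The futility rule is no safeguard: at 15% versus 35% it stops only 5% to 6% of trials. The look already exists, no new data are needed, and the pooled-rate rule keeps type I error at or below 5.2%, against 5.3% for the fixed design.

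Much of this stands. The power losses at 10% to 20% are computed correctly, and the plan has no check on the rate. What does not stand is the step from there to a defect. No document puts the control rate at 15% or 20%. That the 158 patients predate the current bundle is itself inferred, since section 2.0 gives no changeover date. Some changes could lower the rate: section 2.0 says rescue blocks were used as needed, whereas section 4.0 gives controls no second block. The rule can only raise N, so it helps only if the rate moved up.

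**Conclusion.** No change follows. The plan's power is right for the rates it names and is presented as conditional on them; a fixed N based on the centre's own data, with one futility look, is an ordinary phase II design. The exposure is real but hypothetical: power of about 75% to 63% for a 20-point gain if the control rate is 10% to 20%, 71% to 50% if the block converts a fixed share of the remaining patients, and 97% or more if the odds ratio holds.

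Re-estimation would recover 10.3 of the 17.9 points lost in the most favourable reading at a 15% control rate, about a third on the conversion scale, and nothing at low control rates. Its price is up to 51% more evaluable patients and a breach of the screening limit and timeline. That is a choice to enrol more on unsupported rates, which the sponsor may reasonably decline. A table of power by control rate would inform readers but alter no analysis or result. The conclusion would differ only if data under current care showed a control rate well above 5%, and the documents contain none.
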